8.3.5. Electronic Diary

All participants will be required to complete a reactogenicity e-diary after each vaccination given at Visits 1 and 201 through an application installed on a provisioned device or on the participant's own personal device. All participants will be asked to monitor and record local reactions, systemic events, and use of antipyretic medication for 7 days from the day of administration of the study intervention given at Visits 1 and 201. The reactogenicity e-diary allows recording of these assessments only within a fixed time window, thus providing the accurate representation of the participant's experience at that time. Data on local reactions and systemic events reported in the reactogenicity e-diary will be transferred electronically to a third-party vendor, where they will be available for review by investigators and the Pfizer clinicians at all times via an internet-based portal.

At intervals agreed to by the vendor and Pfizer, these data will be transferred electronically into Pfizer's database for analysis and reporting. These data do not need to be reported by the investigator in the CRF, unless the participant missed an e-diary entry and the participant experienced a prompted local reaction or systemic event, in which case any missed entries should be included in the AE CRF.

Investigators (or designee) will be required to review the reactogenicity e-diary data online at frequent intervals as part of the ongoing safety review.

The investigator or designee must obtain stop dates from the participant for any ongoing local reactions, systemic events, or use of antipyretic medication on the last day that the reactogenicity e-diary was completed. The stop dates should be documented in the source documents and the information entered in the CRF.

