For participants experiencing any local reactions (or those with a derived reaction as described in Table 4), the maximum duration (resolution date of reaction - start date of reaction + 1) will be derived.

Resolution of the reaction is the last day on which the reaction is recorded in the e-diary or the date the reaction ends if it is unresolved during the participant e-diary recording period (end date collected on the CRF), unless chronicity is established. If there is no known end date, the duration will be considered unknown and set to "missing." Participants with no reported reactions have no duration.

Onset Day of Each Local Reaction

The onset day of each local reaction will be derived. Onset day is defined as the first day of reporting any severity.

For the onset day of each local reaction, if participants report a change in severity of the local reaction, only the first day of reporting that specific local reaction will be counted.

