6.1.1.2. Sensitivity/Supplementary Analyses

To support the assessment of reactogenicity, the endpoints below, as specified in Section 3.1.1 and Section 3.1.2, will be summarized with the same analysis time point and analysis population:

- Duration (days) of each local reaction and each systemic event after vaccination.
- Onset day of each local reaction and each systemic event after vaccination.
- Presence of each and any severe local reaction and each and any severe systemic event, on each of the 7 days and for "any day (Day 1 through Day 7)."

The presentation of the results will include a basic descriptive summary without 95% CIs (Section 5.2.1).

These continuous endpoints will be summarized by displaying the n, mean, median, standard deviation, minimum, and maximum for each study intervention group and overall, for participants 18 through 64 years of age and ≥65 years of age separately and combined.

In addition, the proportions of participants reporting prompted local reactions and systemic events, by maximum severity level, with any e-diary errors will be included as a supplemental summary for participants 18 through 64 years of age and ≥65 years of age separately and combined.

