3.1.1. Local Reactions and Systemic Events

Local reactions will be assessed at the injection site on the right arm only. Endpoints include both each reaction or event and any reaction or event.

The local reactions, including redness, swelling, and pain at the injection site, and the systemic events, including fever, fatigue (tiredness), headache, muscle pain, vomiting, diarrhea, chills, and joint pain, are reported in the e-diary from Day 1 through Day 7 after vaccination, where Day 1 is the day of vaccination. The e-diary entries from the participant will be the primary data source for these events. However, any related events that are considered local reactions or systemic events starting within 7 days after vaccination, that are recorded in the unplanned CRF or AE CRF, will be consolidated with e-diary data and the data included in the reactogenicity summaries if the participant has any e-diary data recorded.

This section describes derivations with details for the assessment of the reactogenicity data: severity level, duration, and onset day.

Severity and Maximum Severity

The definitions for reactogenicity severity collected from the e-diary and from AEs are described in Appendix 2.

For each local reaction or systemic event after vaccination, the maximum severity will be derived for the collection period (Day 1 through Day 7, where Day 1 is the day of vaccination) as follows:

maximum severity = highest grade (maximum severity) within 7 days after vaccination (Day 1 through Day 7) among severity grades reported for that local reaction or systemic event

Duration (First to Last Day Reported)

The duration (days) of each local reaction or systemic event will be calculated as the number of days from the start of the first reported reaction or event to the resolution of the last reported reaction or event, inclusive. For reactions or events collected in the e-diary, resolution is defined as the last day on which the reaction or event is recorded in the e-diary if the reaction or event lasted 7 days or less, or it is defined as the day on which the reaction or event ended beyond Day 7 (the latter will be collected on the CRF). For reactions and events collected in the AE CRF, the AE end date will be considered the resolution date. For a reaction or event collected in multiple sources, the latest date will be used in calculating the duration. If there is no known resolution/end date, the duration will be reported as unknown or missing.

Onset Day

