6.1.1.2. Sensitivity/Supplementary Analyses

To support the assessment of reactogenicity, the endpoints will be summarized with the same analysis time points and analysis population:

- Duration (days) of each local reaction and each systemic event after vaccination.
- Onset day of each local reaction and each systemic event after vaccination.
- Presence of each local reaction and each systemic event, for "any day (Day 1 through Day 7)." Any severe local reactions or any severe systemic events for "any day (Day 1 through Day 7)."
- The proportion of participants reporting local reactions and systemic events within 7 days after vaccination based only on e-diary data. These continuous endpoints will be summarized by displaying the n, mean, median, standard deviation, minimum, and maximum for each study intervention group for participants 18 through 64 years of age.

Summaries of the proportion of participants with each local reaction and systemic event occurring within 7 days of vaccination (by maximum severity) will also be created using bar charts.

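### Both SAPs treat a reaction's duration as missing when no end date is known, which can understate the mean and especially the maximum in the supplementary duration tables

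*SAP*

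**What the plan says.** Section 6.1.1.2 of each SAP lists "Duration (days) of each local reaction and each systemic event after vaccination" among the sensitivity and supplementary analyses. In Substudy A, "These continuous endpoints will be summarized by displaying the n, mean, median, standard deviation, minimum, and maximum for each study intervention group and overall"; the Substudy B SAP asks for the same six statistics by study intervention group.

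Section 3.1.1 of each SAP sets the end of a reaction in two steps:

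- **Within the diary.** The end is the last day on which the reaction was recorded in the e-diary.
- **Beyond the diary.** The end date comes from the CRF. In Substudy B, "it is defined as the day on which the reaction or event ended beyond Day 7". Substudy A adds an exception: "end date collected on the CRF), unless chronicity is established". It does not say what duration a chronic reaction then receives.

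If neither step yields a date, Substudy B says "If there is no known resolution/end date, the duration will be reported as unknown or missing". Substudy A says "If there is no known end date, the duration will be considered unknown and set to" missing.

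Neither SAP plans a lower-bound value, a censored summary or a required count of unresolved reactions.

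The protocol works to limit the problem. Section 8.3.5 says "The investigator or designee must obtain stop dates from the participant for any ongoing local reactions, systemic events, or use of antipyretic medication" where these are ongoing on the last completed diary day. The visit procedures seek stop dates at Visits 3 and 4 in Substudy A and at Visits 203 and 204 in Substudy B.

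**The concern.** The reactions that reach the rule are not a random sample. A reaction confined to the diary period normally has an end date by definition, so those left without one are mainly reactions that outlasted the diary. Whether the duration is missing therefore depends on the duration itself. Something is still known about each of these reactions: its onset, and the last day on which it was known to be present. That gives a firm lower bound, which the rule discards.

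The maximum is most exposed, because one excluded reaction may be the one that defines it. Most vaccine groups have about 30 participants, so a single case can decide what the table shows. A reader who uses the table to judge persistence of symptoms could conclude that nothing lasted beyond a few days when one reaction was still present at the last contact.

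**Working it through.** The documents give no duration figure, so there is none to reproduce. The check has two parts: which reactions the rule reaches, and what leaving them out does under stated assumptions.

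**1. Which reactions reach the rule**

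| Reaction | End date under section 3.1.1 | Kept in the duration summary? |
|---|---|---|
| Ends within the diary | Last recorded diary day | Yes |
| Participant stops the diary early | Last recorded diary day, on a plain reading | Yes, in effect at its lower bound |
| Outlasts the diary, CRF stop date obtained | CRF date | Yes |
| Outlasts the diary, no stop date obtained | None | No |
| Judged chronic (Substudy A) | Not defined | Unclear |

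The loss is confined to the fourth row, and possibly the fifth. The 6-month telephone contacts (Visits 6 and 205) do not list reactogenicity stop dates. Protocol section 8.4.1 lets follow-up of an event close at stabilisation, which is not an end date. So the fourth row can occur.

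**2. Worked example (all inputs assumed)**

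Take 20 participants with a given reaction. The resolved durations are 5 of 1 day, 7 of 2 days, 4 of 3 days, 2 of 4 days and 1 of 5 days, and one reaction is unresolved. For 2 and 3 unresolved, the longest resolved values are replaced in turn. The resolved totals are:

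- 1 unresolved: 5×1 + 7×2 + 4×3 + 2×4 + 1×5 = 44 days over 19 reactions
- 2 unresolved: 44 − 5 = 39 days over 18
- 3 unresolved: 39 − 4 = 35 days over 17

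Mean under the SAP rule = resolved total ÷ number resolved. Mean with lower bounds = (resolved total + k × L) ÷ 20, where k reactions are unresolved and each has lasted at least L days. L = 8 and L = 28 stand for last contact at about the 1-week or 4-week visit.

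| k | L | SAP mean | SAP maximum | Mean with lower bounds | Maximum |
|---|---|---|---|---|---|
| 1 | 28 | 44/19 = 2.32 | 5 | (44+28)/20 = 3.60 | ≥28 |
| 2 | 28 | 39/18 = 2.17 | 4 | (39+56)/20 = 4.75 | ≥28 |
| 3 | 28 | 35/17 = 2.06 | 4 | (35+84)/20 = 5.95 | ≥28 |
| 1 | 8 | 44/19 = 2.32 | 5 | (44+8)/20 = 2.60 | ≥8 |
| 2 | 8 | 39/18 = 2.17 | 4 | (39+16)/20 = 2.75 | ≥8 |

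The median is 2 days in every row, with or without the unresolved reactions.

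**3. Simulation (assumed distribution)**

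Durations are lognormal with median 2 days and log-SD 0.7 or 1.0, rounded up to whole days.

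| End date unknown for | Log-SD | Dropped | True mean | Mean under SAP rule |
|---|---|---|---|---|
| All reactions past Day 7 | 0.7 | 3.7% | 3.05 | 2.78 |
| All reactions past Day 7 | 1.0 | 10.5% | 3.80 | 2.71 |
| Only those past Day 28 | 0.7 | 0.01% | 3.05 | 3.05 |
| Only those past Day 28 | 1.0 | 0.4% | 3.80 | 3.64 |

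The first two rows are a worst case in which no stop dates are obtained. The last two are nearer to a study that collects them. The median moved by 0 or 1 day. Rounding up puts half of the values at 2 days or less, so the simulated median sits on the edge between 2 and 3 days.

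**4. Cases that do not bias downward**

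If 5% of end dates are lost at random, the mean is unchanged (3.80 and 3.80). If one short reaction starting on Day 7 is dropped, the mean can rise slightly. With 5 reactions of 2 days, 7 of 3, 5 of 4, 2 of 5 and one of 1 day, it goes from 62/20 = 3.10 to 61/19 = 3.21.

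**The case against.** The strongest reply is that little will be lost. Sites must seek stop dates, and they do so at two visits after the diary. Most persistent reactions will therefore get an end date, and the simulation limited to reactions past Day 28 moves the mean by at most 0.16 day (3.80 to 3.64). Duration is a supplementary, descriptive summary with no decision rule attached. The Substudy B wording also allows an unknown category to be displayed. In either substudy, a reader could set the n for duration against the number reporting the reaction and largely recover how many are missing. Substudy B Groups 3 to 5 have up to 120 participants each, so one case has less effect on the mean there. For Substudy B events taken from the AE CRF, missing dates follow sponsor rules that are not in the documents, so their handling cannot be settled here.

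All of this limits the size, and it stands. It does not remove the point. A recovered count says nothing about how long the missing reactions lasted, and the printed maximum is wrong if even one unresolved reaction exceeded it. The Substudy A exception for chronic reactions might have covered these cases, but it assigns no value.

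A reader might infer that every reaction outlasting the diary is lost, or that everyone who leaves early is dropped. The documents support neither: CRF end dates are used after Day 7, and on a plain reading an early leaver keeps a diary-based duration.

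**Conclusion.** The point holds as a minor one. For reactions that persist past Day 7 without a CRF stop date, both SAPs discard a known lower bound. This can understate the mean, and especially the maximum, in the supplementary duration tables. The direction rests on these reactions being longer than the others, which follows from how end dates are assigned; it need not hold for each individual missing date.

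The size cannot be taken from the documents. Under the assumed examples, one unresolved reaction among 20 raises the mean by at least 0.28 day (2.60 − 2.32) if last known present at 8 days, or by at least 1.28 days (3.60 − 2.32) at 28 days. The maximum changes from 5 to at least 8 or at least 28. Few such reactions are expected.

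Two stronger conclusions are tempting. One is that the median is also materially biased; in these checks it barely moves. The other is that the primary reactogenicity results are affected. They are not: the rule concerns duration only, so the proportion with each reaction and the maximum severity are unchanged.

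**What to change.** In section 3.1.1 of both SAPs, add for a reaction with no known end date:

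- Keep the last day on which it was known to be present, and use it as a lower bound for the duration.
- Report, by study intervention group, the number of reactions unresolved at last contact.
- Show the maximum as at least x days when it comes from such a reaction.
- Label the mean either as excluding unresolved reactions or as a lower bound that includes them.

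In the Substudy A SAP, also state what duration is assigned once a reaction is judged chronic. A Kaplan-Meier median time to resolution could be added, but it is optional.

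The cost is a few lines of text and a little programming for a supplementary table. No new data collection is needed. The one drawback is that, where unresolved reactions exist, the mean needs a footnote and is no longer a plain average of known durations.

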3.1.2. Adverse Events

Standard algorithms for handling missing AE dates will be applied (see Section 5.3). AEs will be categorized according to MedDRA terms. The time period for actively eliciting and collecting AEs and SAEs ("active collection period") for each participant begins from the time the participant provides informed consent, which is obtained before the participant's participation in the study through the 4-week follow-up visit. Additionally, any AEs occurring up to 48 hours after the blood draws at Visit 204 (4-week follow-up visit) must be recorded on the CRF.

SAEs will be collected from the time the participant provides informed consent to approximately 6 months after the participant's study vaccination.

Events occurring prior to vaccination will be excluded from the AE analyses but may be listed out.

3.1.3. Laboratory Data

The following safety laboratory test will be performed at the times defined in the schedule of activities of the protocol.

Substudy B Enrollment	
Hematology Chemistry	
N/A	Cardiac troponin I

Clinically significant abnormal laboratory findings should be recorded in the AE CRF. Any troponin I value ≥0.30 ng/mL is considered abnormal.

3.1.4. ECG Data

ECGs will be collected at the times specified for the substudy.

ECG data will be submitted to a central laboratory for evaluation.

ECG abnormalities consistent with probable or possible myocarditis or pericarditis are those judged as such by a cardiologist.

3.2. Secondary Endpoints

Blood samples will be collected for immunogenicity assessments prior to vaccination and at 4 weeks after vaccination.

Influenza

- HAI titers for each strain before vaccination and at each time point after vaccination.
- HAI titer fold rises for each strain from before vaccination to each time point after vaccination.
- HAI seroconversion for each strain at each time point after vaccination.
- HAI titers ≥1:40 for each strain before vaccination and at each time point after vaccination.

Seroconversion is defined as an HAI titer <1:10 prior to vaccination and $\ge 1:40$ at the time point of interest or an HAI titer of $\ge 1:10$ prior to vaccination with at least a 4-fold rise at the time point of interest.

Fold rises are defined as ratios of the results after vaccination to the results before vaccination. The calculations of fold rises are limited to participants with nonmissing values at both time points.

The strains mentioned above for qIRV- or QIV-related study interventions refer to the matched seasonal strains (CCI) and (CCI) recommended by WHO, and the strains mentioned above for tIRV-related study interventions refer to the matched seasonal strains (CCI) recommended by WHO.

SARS-CoV-2

- SARS-CoV-2—neutralizing titers for each strain before vaccination and at each time point after vaccination.
- SARS-CoV-2—neutralizing titer fold rise for each strain from before vaccination to each time point after vaccination.
- SARS-CoV-2 seroresponse for each strain at each time point after vaccination.

Seroresponse is defined as achieving a \geq 4-fold rise from baseline (before the study vaccination). If the baseline measurement is below the LLOQ, the postvaccination measure of \geq 4 × LLOQ is considered seroresponse.

The strain mentioned above refers to SARS-CoV-2 (Omi BA.4/BA.5) or the SARS-CoV-2 reference strain (original).

Fold rises are defined as ratios of the results after vaccination to the results before vaccination. The calculations of fold rises are limited to participants with nonmissing values at both time points.

3.3. Other Endpoints

- SARS-CoV-2-neutralizing titers for each strain of emergent variants at each time point.
- SARS-CoV-2—neutralizing titer fold rise for each strain of emergent variants from before vaccination to each time point after vaccination.
- SARS-CoV-2 seroresponse for each strain of emergent variants at each time point after vaccination.

3.4. Baseline Variables

Age at the time of vaccination (in years) will be derived based on the participant's birthday. For example, if the vaccination day is 1 day before the participant's 19th birthday, the participant is 18 years old.

For reporting of race, where more than 1 category is selected for race, the participant would be counted under the category "multiracial" for analysis.

Medical history will be categorized according to MedDRA.

The name and date of administration for any concomitant medications and nonstudy vaccinations received will be collected.

3.4.1. E-Diary Completion

An e-diary will be considered transmitted if any data for the 3 local reactions (redness, swelling, and pain at the injection site), 8 systemic events (fever, vomiting, diarrhea, headache, fatigue, chills, new or worsening muscle pain, and new or worsening joint pain), or use of antipyretic/pain medication to treat symptoms, are present on any day. If all data are missing for all items on the e-diary, for all days following vaccination, the e-diary will be considered not transmitted.

An e-diary will be considered completed if all expected data for all days are available (ie, not missing) and data are valid. Otherwise, the e-diary will be considered incomplete. For any given day, an e-diary will be considered complete if all expected data are available.

The following e-diary compliance variables will be provided:

- Compliance per day: The numerator is the number of participants who completed (transmitted) the e-diary on a given day (Day 1 through Day 7, where Day 1 is the day of vaccination) and the denominator is the total number of participants who received the vaccination.
- At least X days: The numerator is the number of participants who completed (transmitted) the e-diary on X days and the denominator is the total number of participants who received a vaccination (X = Day 1 through Day 7; compliance will be computed for each value of X).
- All 7 days: The numerator is the number of participants who completed (transmitted) the e-diary on all 7 days and the denominator is the total number of participants who received a vaccination.

3.5. Safety Endpoints

Refer to Section 3.1.

4. ANALYSIS SETS (POPULATIONS FOR ANALYSIS)

Data for all participants will be assessed to determine if participants meet the criteria for inclusion in each analysis population prior to unblinding and releasing the database and classifications will be documented per standard operating procedures.

Population	Description
Screened	All participants who sign the ICD.
Randomized	All participants who are assigned a randomization number in the IRT system.

Population	Description
Evaluable immunogenicity	All participants who are eligible, receive the study intervention to which they were randomized, have blood drawn for assay testing within the specified time frame after vaccination (26-35 days after vaccination), have at least 1 valid and determinate assay result at the 4-week postvaccination visit, and have no major protocol violations.
mITT immunogenicity	All randomized participants who receive the study intervention and have at least 1 valid and determinate assay result after vaccination.
Safety	All participants who receive the study intervention.

For determination of the evaluable immunogenicity population(s), the last criteria of exclusions due to major protocol violations will be determined via clinical review. The remainder of the criteria will be determined programmatically.

A major protocol violation is a protocol violation that, in the opinion of the sponsor's global medical monitor, would materially affect assessment of immunogenicity, eg, participant receipt of a prohibited vaccine, medication that might affect immune response, or a medication error with suspected decrease in potency of the vaccine. The global medical monitor from the sponsor will identify those participants with a protocol violation prior to any immunogenicity analysis in the study.

For safety, reporting will be as administered and, for immunogenicity, reporting will be as randomized.

For all the immunogenicity endpoints, the analysis will be based on the evaluable immunogenicity population.

An additional analysis may be performed based on the mITT population if there is a large enough difference (>10%) in sample size between the mITT population and the evaluable immunogenicity population.

